4.2.1 Cytarabine

Cytarabine will be administered on day 1, dose-adjusted for age (<60 years: 2 gm/m² IV Q12hours days 1-5; ≥ 60 years: 1.5 gm/m² IV Q12hours days 1-5). If organ dysfunction (i.e. renal dysfunction) arises during cytarabine administration, cytarabine can be dose-reduced after discussion with study team and PI. Cytarabine will be administered as an IV infusion over approximately 2 hours, per institutional guidelines. To prevent kerato-conjunctivitis, dexamethasone 0.1%

ophthalmic eye drops will be administered to both eyes Q6 hours at least 1 hour prior to cytarabine initiation and continued through day 12 of therapy (see Supportive Care).

Cerebellar exams should be performed prior to each dose of cytarabine. Any new symptoms suggestive of cerebellar toxicity should result in temporary discontinuation of cytarabine until symptoms resolve, as per institutional policy.

4.2.2 Pembrolizumab

All patients will receive pembrolizumab 200 mg IV for 1 dose on day 14 of therapy, as long as they have received >50% of planned doses of cytarabine (see 4.2.1). Pembrolizumab will be administered as a 30 minute IV infusion. Sites should make every effort to target infusion timing to be as close to 30 minutes as possible. However, given the variability of infusion pumps from site to site, a window of -5 minutes and +10 minutes is permitted (i.e., infusion time is 30 minutes: -5 min/+10 min). The Pharmacy Manual contains specific instructions for the preparation of the pembrolizumab infusion fluid and administration of infusion solution. This manual is provided as a document separate from the protocol.

Management of Infusion Reactions: Signs and symptoms usually develop during or shortly after drug infusion and generally resolve completely within 24 hours of completion of infusion. Refer to the table below for infusion reaction treatment guidelines:

NCI CTCAE Grade	Treatment	Premedication at subsequent dosing
Grade 1 Mild reaction; infusion interruption not indicated; intervention not indicated	Increase monitoring of vital signs as medically indicated until the subject is deemed medically stable in the opinion of the investigator.	None
Grade 2 Requires infusion interruption but responds promptly to symptomatic treatment (e.g., antihistamines, NSAIDS, narcotics, IV fluids); prophylactic medications indicated for < =24 hrs	Stop Infusion and monitor symptoms. Additional appropriate medical therapy may include but is not limited to: IV fluids Antihistamines NSAIDS Acetaminophen Narcotics Oxygen Pressors Corticosteroids Epinephrine Increase monitoring of vital signs as medically indicated until the subject is	Subject may be premedicated 1.5h (± 30 minutes) prior to infusion of pembrolizumab with: Diphenhydramine 50 mg po (or equivalent dose of antihistamine). Acetaminophen 500-1000 mg po (or equivalent dose of antipyretic).

NCI CTCAE Grade	Treatment	Premedication at subsequent dosing
	
deemed medically stable in the opinion of the investigator. If symptoms resolve within one hour of stopping drug infusion, the infusion may be restarted at 50% of the original infusion rate (e.g., from 100 mL/hr to 50 mL/hr). Otherwise dosing will be held until symptoms resolve and the subject should be premedicated for the next scheduled dose.
 
Subjects who develop Grade 2 toxicity despite adequate premedication should be permanently discontinued from further trial treatment administration.
	

Grades 3 or 4 Grade 3: Prolonged (i.e., not rapidly responsive to symptomatic medication and/or brief interruption of infusion); recurrence of symptoms following initial improvement; hospitalization indicated for other clinical sequelae (e.g., renal impairment, pulmonary infiltrates) Grade 4: Life-threatening; pressor or ventilatory support indicated
	
Stop Infusion. Additional appropriate medical therapy may include but is not limited to: IV fluids, Antihistamines, NSAIDS Acetaminophen, Narcotics, Oxygen, Pressors, Corticosteroids Epinephrine
 
Increase monitoring of vital signs as medically indicated until the subject is deemed medically stable in the opinion of the investigator. Hospitalization may be indicated. Subject is permanently discontinued from further trial treatment administration.
	
No subsequent dosing

Appropriate resuscitation equipment should be available in the room and a physician readily available during the period of drug administration.
		

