2.4.2 Secondary Endpoints

- The rate of unacceptable toxicity is defined as drug-related grade 3 non-hematologic toxicity (with exception of infusion reactions, rash, fever, infection, nausea, fatigue, and anorexia) persisting for >7 days with supportive care, or any drug-related non-hematologic grade ≥ 4 toxicity (excluding infection). Toxicity will be classified and graded according to National Cancer Institute's (NCI) Common Terminology Criteria for

Adverse Events (CTCAE, version 4.0). Any patient who receives pembrolizumab treatment on this protocol will be evaluable for toxicity.

- Clinician assessed toxicity of HiDAC followed by pembrolizumab, and toxicity of pembrolizumab maintenance monotherapy classified and graded according to NCI CTCAEv4
- PR+CR+CRi as determined by International European LeukemiaNet Guidelines in AML²¹
- RFS will be defined as time from day 1 of CR/CRi to relapse or death from any cause.
- PFS will be defined as time from day 1 of response (i.e., PR/CR/CRi) to progression or death from any cause.
- OS will be defined as time from day 1 of treatment until date of last known follow up or death of any cause.

[REDACTED]

[REDACTED]

[REDACTED]

[REDACTED]

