
Grade 1 Mild reaction; infusion interruption not indicated; intervention not indicated
	
Increase monitoring of vital signs as medically indicated until the participant is deemed medically stable in the opinion of the investigator.
	
None

Grade 2 Requires therapy or infusion interruption but responds promptly to symptomatic treatment (e.g., antihistamines, NSAIDs, narcotics, IV fluids); prophylactic medications indicated for ≤24 hrs
	
Stop Infusion. Additional appropriate medical therapy may include but is not limited to: IV fluids Antihistamines NSAIDs Acetaminophen Narcotics Increase monitoring of vital signs as medically indicated until the participant is deemed medically stable in the opinion of the investigator. If symptoms resolve within 1 hour of stopping drug infusion, the infusion may be restarted at 50% of the original infusion rate (e.g. from 100 mL/hr to 50 mL/hr). Otherwise dosing will be held until symptoms resolve and the participant should be premedicated for the next scheduled dose. Participants who develop Grade 2 toxicity despite adequate premedication should be permanently discontinued from further study drug treatment
	
Participant may be premedicated 1.5h (± 30 minutes) prior to infusion of _____ with: Diphenhydramine 50 mg po (or equivalent dose of antihistamine). Acetaminophen 500-1000 mg po (or equivalent dose of analgesic).

Grades 3 or 4 Grade 3: Prolonged (i.e., not rapidly responsive to symptomatic medication and/or brief interruption of infusion); recurrence of symptoms following initial improvement; hospitalization indicated for other clinical sequelae (e.g., renal impairment, pulmonary infiltrates) Grade 4: Life-threatening; pressor or ventilatory support indicated
	
Stop Infusion. Additional appropriate medical therapy may include but is not limited to: Epinephrine** IV fluids Antihistamines NSAIDs Acetaminophen Narcotics Oxygen Pressors Corticosteroids Increase monitoring of vital signs as medically indicated until the participant is deemed medically stable in the opinion of the investigator. Hospitalization may be indicated. **In cases of anaphylaxis, epinephrine should be used immediately. Participant is permanently discontinued from further study drug treatment.
	
No subsequent dosing

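### The section 4.2.2 infusion-reaction table lists pressors as a Grade 2 treatment but defines Grade 4 by the need for pressors, and Appendix B Table 4 differs from it with no precedence rule

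*Combined protocol and SAP*

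**What the plan says.** Protocol section 4.2.2 contains an infusion-reaction table with three columns: CTCAE grade with its definition, treatment, and premedication at later doses.

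- **Grade 2, definition.** "Requires infusion interruption but responds promptly to symptomatic treatment (e.g., antihistamines, NSAIDS, narcotics, IV fluids"). Pressors are not among the examples.
- **Grade 2, treatment.** The list opens with "Additional appropriate medical therapy may include but is not limited to" and runs "IV fluids Antihistamines NSAIDS Acetaminophen Narcotics Oxygen Pressors Corticosteroids Epinephrine".
- **Grade 2, consequence.** "If symptoms resolve within one hour of stopping drug infusion, the infusion may be restarted at 50% of the original infusion rate".
- **Grade 4, definition.** "Grade 4: Life-threatening; pressor or ventilatory support indicated".
- **Grade 3 or 4, consequence.** "Subject is permanently discontinued from further trial treatment administration".

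Section 11.2 (Appendix B) has its own infusion-reaction table, Table 4. Section 4.4.6 sends sites to 4.2.2 for infusion reactions, while the Appendix B text says that the guidelines are in Table 4. No section says which table governs if they differ.

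Section 2.4.2 defines unacceptable toxicity in two limbs. The first is Grade 3 non-hematologic toxicity persisting beyond 7 days, from which infusion reactions are excepted. The second is "any drug-related non-hematologic grade ≥ 4 toxicity (excluding infection"), with no infusion-reaction exception. Section 8.2 uses the same structure for the stopping boundary.

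**The concern.** One treatment has two roles in one table. At Grade 2 it is a listed option in a row that permits the infusion to resume. At Grade 4 the need for it defines the grade, in a row that ends dosing. Suppose a patient is given a pressor and settles within the hour. Someone working from the treatment column could handle that patient under the Grade 2 row; someone working from the definition column would not. The second table adds to the uncertainty, because its Grade 2 row does not name pressors at all.

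The first thing at stake is re-exposure after a reaction that needed rescue treatment. The table applies from the day 14 induction dose onward, and the trial is multicenter, so sites could follow different tables. The second is how consistently the toxicity endpoint is recorded. A drug-related Grade 4 reaction is an unacceptable toxicity and a Grade 2 reaction is not.

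**Working it through.** No arithmetic applies, because the plan gives no figure on this point. The check sets the two tables side by side and then follows the grade into the endpoint.

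| Element | Section 4.2.2 table | Appendix B Table 4 |
|---|---|---|
| Grade 2 definition | Infusion interruption needed, with prompt response to symptomatic treatment | Either therapy or infusion interruption needed, with prompt response |
| Grade 2 treatments named | IV fluids through narcotics, then oxygen, pressors, corticosteroids, epinephrine | IV fluids through narcotics only |
| Grade 2 restart at half rate within one hour | Allowed | Allowed |
| Grade 4 definition | Pressor or ventilatory support indicated | Same |
| Pressors named at Grade 3 or 4 | Yes | Yes |
| Grade 3 or 4 consequence | Permanent discontinuation | Permanent discontinuation |
| Anaphylaxis instruction | None | "In cases of anaphylaxis, epinephrine should be used immediately" |

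**Step 1: within 4.2.2.** Pressors are named in the Grade 2 treatment cell, and the need for pressor support is part of the Grade 4 definition. The two rows have opposite consequences. This inconsistency does not depend on Appendix B.

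**Step 2: between the tables.** Four treatments named at Grade 2 in 4.2.2 are absent from the Grade 2 row of Table 4. The Grade 2 definitions also differ. Take a reaction that is treated without interrupting the infusion. It can be Grade 2 under Table 4. Under 4.2.2 it meets neither Grade 1, which requires that no intervention be indicated, nor Grade 2, which requires interruption.

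**Step 3: which table is operative.** Both are. Section 4.4.6 points to 4.2.2, Appendix B points to Table 4, and there is no precedence rule.

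**Step 4: from grade to endpoint.** In 2.4.2, 8.2 and 8.3 the infusion-reaction exception belongs to the Grade 3 limb.

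- Recorded as Grade 2: below both limbs, so not counted.
- Recorded as Grade 3: excepted, so not counted.
- Recorded as Grade 4 and drug-related: counted in 2.4.2 and toward the 8.2 boundary. If it occurs in induction, it also bars maintenance under 4.3.

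The Grade 2 to Grade 4 distinction, which the 4.2.2 table blurs, is therefore one that changes the count.

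**The case against.** The strongest reply is that the left-hand column assigns the grade and the treatment column applies only afterwards. On that reading a patient for whom pressor support is indicated is Grade 4 in either table, and a name in an optional list cannot change this. The reply is sound as a reading of the grade definitions, and it rules out a stronger claim that a reader might infer: that the protocol contains two conflicting definitions of Grade 4. It does not, since the definition is the same in both tables. What the reply leaves unexplained is why pressors are printed at Grade 2 at all. It resolves the conflict only by disregarding that entry, and staff managing an acute reaction should not have to make that inference.

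Second, both treatment lists are expressly open. This also stands. It would be wrong to infer that Appendix B forbids pressors, oxygen, corticosteroids or epinephrine at Grade 2, because omission from an open list is not a prohibition. Likewise the anaphylaxis sentence in Table 4 adds guidance and contradicts nothing; 4.2.2 already lists epinephrine at Grade 3 or 4.

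Third, toxicity is graded by CTCAE version 4.0, and no section makes the treatment list a grading rule for 2.4.2 or 8.2. That is correct, so the endpoint effect arises only if the Grade 2 entry leads someone to record the lower grade. The maintenance bar in 4.3 adds little, because a Grade 4 reaction already ends dosing under the table.

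Fourth, a reader might infer that one regraded event could decide whether accrual halts. It could do so only when the count is already one short of the boundary. The 8.2 limit of 3 at n = 3 needs 3 − 1 = 2 other events, and the limit of 5 at n = 6 to 8 needs 5 − 1 = 4. Any single event has that property, and the documents say nothing about how often pressor-treated reactions occur.

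**Conclusion.** This is an internal inconsistency in an operative safety instruction. The main fault lies within the 4.2.2 table; the differing Appendix B table and the lack of a precedence rule add to it. Strict reading of the grade definitions leads to Grade 4, but the printed Grade 2 entry points toward the handling that allows a restart.

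The size can be stated only per event. For a reaction in which a pressor is used, the row chosen separates a permitted restart from permanent discontinuation. If the reaction is judged drug-related, the recorded grade also separates a counted unacceptable toxicity from an uncounted one. No frequency is claimed, and no effect on the operating characteristics of the 8.2 boundary. The endpoint part assumes that the Grade 2 entry influences the grade recorded at the site; the inconsistency in the text needs no such assumption. Nothing here says which clinical rule is right.

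**What to change.** Reconcile the 4.2.2 table with Appendix B Table 4, covering the grade definitions, the treatments named in each row and the anaphylaxis instruction, so that a single infusion-reaction table applies. Have 4.2.2, 4.4.6 and Appendix B all refer to that table. The sponsor decides which clinical content it carries.

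The cost is amendment wording and its circulation to sites. The sample size, the 8.2 boundary, the endpoint definitions and the data collected do not change.

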4.2.2.1 Contraception

Pembrolizumab may have adverse effects on a fetus in utero. Furthermore, it is not known if pembrolizumab has transient adverse effects on the composition of sperm. For this trial, male subjects will be considered to be of non-reproductive potential if they have azoospermia (whether due to having had a vasectomy or due to an underlying medical condition).

Female subjects will be considered of non-reproductive potential if they are either:

(1) postmenopausal (defined as at least 12 months with no menses without an alternative medical cause; in women < 45 years of age a high follicle stimulating hormone (FSH) level in the postmenopausal range may be used to confirm a post-menopausal state in women not using hormonal contraception or hormonal replacement therapy. In the absence of 12 months of amenorrhea, a single FSH measurement is insufficient.);

OR

(2) have had a hysterectomy and/or bilateral oophorectomy, bilateral salpingectomy or bilateral tubal ligation/occlusion, at least 6 weeks prior to screening;

OR

(3) have a congenital or acquired condition that prevents childbearing.

Female and male subjects of reproductive potential must agree to avoid becoming pregnant or impregnating a partner, respectively, while receiving study drug and for 120 days after the last dose of study drug by complying with one of the following:

(1) practice abstinence[†] from heterosexual activity;

OR

(2) use (or have their partner use) acceptable contraception during heterosexual activity.

Acceptable methods of contraception are[‡]:

Single method (one of the following is acceptable):

- intrauterine device (IUD)
- vasectomy of a female subject's male partner
- contraceptive rod implanted into the skin

Combination method (requires use of two of the following):

- diaphragm with spermicide (cannot be used in conjunction with cervical cap/spermicide)
- cervical cap with spermicide (nulliparous women only)
- contraceptive sponge (nulliparous women only)
- male condom or female condom (cannot be used together)
- hormonal contraceptive: oral contraceptive pill (estrogen/progestin pill or progestin-only pill), contraceptive skin patch, vaginal contraceptive ring, or subcutaneous contraceptive injection

[†]Abstinence (relative to heterosexual activity) can be used as the sole method of contraception if it is consistently employed as the subject's preferred and usual lifestyle and if considered acceptable by local regulatory agencies and ERCs/IRBs. Periodic abstinence (e.g., calendar, ovulation, sympto-thermal,

post-ovulation methods, etc.) and withdrawal are not acceptable methods of contraception.

‡If a contraceptive method listed above is restricted by local regulations/guidelines, then it does not qualify as an acceptable method of contraception for subjects participating at sites in this country/region.

Subjects should be informed that taking the study medication may involve unknown risks to the fetus (unborn baby) if pregnancy were to occur during the study. In order to participate in the study subjects of childbearing potential must adhere to the contraception requirement (described above) from the day of study medication initiation (or 14 days prior to the initiation of study medication for oral contraception) throughout the study period up to 120 days after the last dose of trial therapy. If there is any question that a subject of childbearing potential will not reliably comply with the requirements for contraception, that subject should not be entered into the study.

4.3 Maintenance Phase

Patients who achieve a PR, CR, or CRi (see section 6.9) will receive pembrolizumab 200 mg IV Q3weeks on an outpatient basis. In order to qualify for pembrolizumab maintenance, all patients will be required to meet laboratory eligibility criteria as outlined in Section 3.1.7 and prior drug-related toxicities must have resolved to \leq grade 1 or baseline. Any patient experiencing unacceptable toxicity during induction, as defined in section 2.4.2, will not be eligible for maintenance, but will be discontinued from protocol-directed therapy and followed-up per protocol. In those who have achieved a CR or PR, pembrolizumab maintenance will begin 10-60 days following full hematologic recovery (absolute neutrophil count \geq 1,000/mcL and platelet count \geq 100,000/mcL). Patients who achieve CRi will begin maintenance pembrolizumab 10-60 days following a bone marrow biopsy disease assessment after induction phase (a repeat bone marrow biopsy should be performed if CRi patients subsequently achieve full hematologic recovery prior to pembrolizumab maintenance, as detailed in Section 4.2: Induction Phase). Patients eligible to receive maintenance therapy should begin maintenance as early as possible (\geq 10 days after hematologic recovery occurs, and once recovery from drug-related toxicities \leq grade 1 or baseline). Those who do not receive maintenance therapy by day 60 of hematologic recovery or by day 60 of post-induction bone marrow biopsy in CRi patients will be taken off study protocol.

All patients who continue pembrolizumab maintenance therapy will have disease assessments with bone marrow biopsies after every 4 cycles of treatment (i.e., every 12 weeks) for the first year, and then after every 6 cycles of treatment (i.e. every 18 weeks) during years 1-2. If there is suspicion for disease progression, a disease assessment via bone marrow biopsy will occur at any time during the maintenance phase. Patients will continue pembrolizumab 200 mg IV Q3weeks

for up to 2 years (i.e., 34 cycles of treatment) until disease progression, unacceptable toxicity, receipt of allogeneic stem cell transplantation or investigator and/or patient chooses to discontinue treatment.

Patients will be eligible to undergo an allogeneic stem cell transplantation after induction phase. Pembrolizumab maintenance can be continued prior to an allogeneic stem cell transplant. The allogeneic stem cell infusion day 0 should occur >21 days after the last infusion of pembrolizumab.

4.3.1 Toxicities and Dose Modifications for Pembrolizumab Maintenance

Adverse events (both non-serious and serious) associated with pembrolizumab exposure may represent an immunologic etiology. These adverse events may occur shortly after the first dose or several months after the last dose of treatment. Pembrolizumab must be withheld for drug-related toxicities and severe or life-threatening AEs as per Table 3 below. See section 4.4 for supportive care guidelines, including use of corticosteroids.

Dosing interruptions are permitted in the case of medical / surgical events or logistical reasons not related to study therapy (e.g., elective surgery, unrelated medical events, patient vacation, and/or holidays). Subjects should be placed back on study therapy within 3 weeks of the scheduled interruption, unless otherwise discussed with the Sponsor. The reason for interruption should be documented in the patient's study record.

If a dose of pembrolizumab is delayed, then the subsequent dose should be administered 3 weeks later. Patients may receive up to 1 year of treatment with pembrolizumab beginning on day 1 of maintenance therapy. In the event of dose delays/interruptions, subjects may not receive more than 1 total year of treatment beginning with day 1 of maintenance therapy.

Table 3. Dose Modifications

General instructions:				

 1. Corticosteroid taper should be initiated upon AE improving to Grade 1 or less and continue to taper over at least 4 weeks. 2. For situations where pembrolizumab has been withheld, pembrolizumab can be resumed after AE has been reduced to Grade 1 or 0 and corticosteroid has been tapered. Pembrolizumab should be permanently discontinued if AE does not resolve within 12 weeks of last dose or corticosteroids cannot be reduced to ≤ 10 mg prednisone or equivalent per day within 12 weeks. 3. For severe and life-threatening irAEs, IV corticosteroid should be initiated first followed by oral steroid. Other immunosuppressive treatment should be initiated if irAEs cannot be controlled by corticosteroids. 				
Immune-related AEs	Toxicity grade or conditions	Action taken to pembrolizumab	irAE management with corticosteroid and/or other therapies	Monitor and follow-up

Amendment 07

	(CTCAEv4.0)			
Pneumonitis	Grade 2	Withhold	
 Administer corticosteroids (initial dose of 1-2 mg/kg prednisone or equivalent) followed by taper 	
 Monitor participants for signs and symptoms of pneumonitis Evaluate participants with suspected pneumonitis with radiographic imaging and initiate corticosteroid treatment Add prophylactic antibiotics for opportunistic infections
	Grade 3 or 4, or recurrent Grade 2	Permanently discontinue		
Diarrhea / Colitis	Grade 2 or 3	Withhold	
 Administer corticosteroids (initial dose of 1-2 mg/kg prednisone or equivalent) followed by taper 	
 Monitor participants for signs and symptoms of enterocolitis (ie, diarrhea, abdominal pain, blood or mucus in stool with or without fever) and of bowel perforation (ie, peritoneal signs and ileus). Participants with \geq Grade 2 diarrhea suspecting colitis should consider GI consultation and performing endoscopy to rule out colitis. Participants with diarrhea/colitis should be advised to
	Grade 4	Permanently discontinue		

				drink liberal quantities of clear fluids. If sufficient oral fluid intake is not feasible, fluid and electrolytes should be substituted via IV infusion.
AST / ALT elevation or Increased bilirubin	Grade 2	Withhold	
 Administer corticosteroids (initial dose of 0.5- 1 mg/kg prednisone or equivalent) followed by taper 	
 Monitor with liver function tests (consider weekly or more frequently until liver enzyme value returned to baseline or is stable)
	Grade 3 or 4	Permanently discontinue	
 Administer corticosteroids (initial dose of 1-2 mg/kg prednisone or equivalent) followed by taper 	
Type 1 diabetes mellitus (T1DM) or Hyperglycemia	Newly onset T1DM or Grade 3 or 4 hyperglycemia associated with evidence of β -cell failure	Withhold	
 Initiate insulin replacement therapy for participants with T1DM Administer anti-hyperglycemic in participants with hyperglycemia 	
 Monitor participants for hyperglycemia or other signs and symptoms of diabetes.
Hypophysitis	Grade 2	Withhold	
 Administer corticosteroids and initiate hormonal replacements as clinically indicated. 	
 Monitor for signs and symptoms of hypophysitis (including hypopituitarism and adrenal insufficiency)
	Grade 3 or 4	Withhold or permanently discontinue ¹		
Hyperthyroidism	Grade 2	Continue	
 Treat with non-selective beta-blockers (eg, propranolol) or thionamides as appropriate 	
 Monitor for signs and symptoms of thyroid disorders.
	Grade 3 or 4	Withhold or permanently discontinue ¹		
Hypothyroidism	Grade 2-4	Continue	
 Initiate thyroid replacement hormones (eg, levothyroxine or liothyronine) per standard of care 	
 Monitor for signs and symptoms of thyroid disorders.

Nephritis and Renal dysfunction	Grade 2	Withhold	
 Administer corticosteroids (prednisone 1-2 mg/kg or equivalent) followed by taper. 	
 Monitor changes of renal function
	Grade 3 or 4	Permanently discontinue		
Myocarditis	Grade 1 or 2	Withhold	
 Based on severity of AE administer corticosteroids 	
 Ensure adequate evaluation to confirm etiology and/or exclude other causes
	Grade 3 or 4	Permanently discontinue		
All other immune-related AEs	Intolerable/persistent Grade 2	Withhold	
 Based on type and severity of AE administer corticosteroids 	
 Ensure adequate evaluation to confirm etiology and/or exclude other causes
	Grade 3	Withhold or discontinue based on the type of event. Events that require discontinuation include and not limited to: Guillain-Barre Syndrome, encephalitis		
	Grade 4 or recurrent Grade 3	Permanently discontinue		

1. Withhold or permanently discontinue pembrolizumab is at the discretion of the investigator or treating physician.
 
NOTE: For participants with Grade 3 or 4 immune-related endocrinopathy where withhold of pembrolizumab is required, pembrolizumab may be resumed when AE resolves to \leq Grade 2 and is controlled with hormonal replacement therapy or achieved metabolic control (in case of T1DM).
				

